#### 2.2.2 Secondary Endpoints

Secondary endpoints include, but are not limited to:

- Levels of acute phase reactant CRP over 35 days follow-up
- Length of hospitalisation from baseline (days)
- Survival at Day35, mortality data collected from EPIC database for both HCs and randomised individuals
- White blood cell count over 7 days follow-up
- Neutrophil count over 7 days follow-up
- Lymphocyte count over 7 days follow-up
- Monocyte count over 7 days follow-up
- Eosinophil count over 7 days follow-up
- Basophil count over 7 days follow-up
- Procalcitonin over 7 days follow-up
- D-dimer count over 7 days follow-up
- Blood pressure over 7 days follow-up
- Pulse rate over 7 days follow-up
- Temperature over 7 days follow-up
- Respiratory rate over 7 days follow-up
- Time on Oxygen over 7 days follow-up
- Time on Oxygen over 35 days follow-up
- Proportion of individuals with Pneumonia over 7 days follow-up
- Ordinal score (WHO scoring tool) over 7 days follow-up (including randomized individuals only)
- Proportion of individuals on Mechanical Ventilation (MV) over 7 days follow-up
- Time on MV over 7 days follow-up
- Length of ICU stay (hours) over 7 days follow-up
- Proportion of individuals with Pneumonia over 35 days follow-up
- Proportion of individuals on Mechanical Ventilation (MV) over 35 days follow-up
- Time on MV over 35 days follow-up
- Length of ICU stay (hours) over 35 days follow-up

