### 4. PLANNED ANALYSES

There are two planned analyses, an interim analysis after 12 randomised individuals have completed Day7 follow-up and the final analysis, once all randomised individuals have completed follow-up (which is the minimum of discharge, death or 35 days after randomisation). At the interim analysis, only the primary endpoint and safety data will be examined, and no secondary or exploratory endpoints. A promising zones approach [1] (see Section 12 for details) will be followed at the interim analysis stage to identify the conditional power and make a decision as to whether to continue enrolment up to the planned 40 individuals randomised, or whether to increase the planned sample size up to a maximum of 48 randomised individuals. See Section 12 for details.

After the final randomised participant has completed follow-up, a more complete analysis will be undertaken, including examination of endpoints relating to the primary, secondary and exploratory objectives. A full safety analysis will also be carried out at this stage.

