For the following secondary endpoints, a survival analysis will be conducted. The number of events by arm will be compared. The time to event data will be censored at 28 days post last dose (Day35) for the randomised participants and at 35 days after baseline, or the date of the last electronic record, whichever is earlier, for the historical control group. If median time-to-event times exist, the Kaplan-Meier method will be used to estimate the median time-to-event times and the associated 95% confidence intervals. The survival model will include treatment as a stratification variable and significance assessed using a log-rank test. A Cox proportional hazards model will be used to generate a hazard ratio and associated confidence intervals, adjusting for age, baseline CRP value (defined as the last CRP measurement prior to randomisation, or the first CRP following Dexamethasone for HCs) and treatment as a main effect. For the time to discharge from hospital analysis, data will be censored if the participant dies prior to discharge at the date of death.

- Survival at Day35
- Time to discharge from hospital from baseline (days) to Day 35

For the following secondary endpoint, a logistic regression model will be fitted, with age, gender, BMI baseline CRP value (defined as the last CRP measurement prior to randomisation, or the first CRP

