## **Exploristics Limited**

# Identifier: EXP20012

Clinical Study Identifier: 132333 following Dexamethasone for HCs), whether they have a key comorbidity, defined as one or more of

hypertension, diabetes or cardiovascular disease as covariates and treatment included as covariates.

- Proportion of individuals on Mechanical Ventilation (MV) over 7 days follow-up
- Proportion of individuals on Mechanical Ventilation (MV) over 35 days follow-up
- Proportion of individuals with Pneumonia over 7 days follow-up
- Proportion of individuals with Pneumonia over 35 days follow-up

For the following secondary endpoints, a linear regression model will be fitted, with age, gender, BMI, baseline CRP (defined as the last CRP measurement prior to randomisation, or the first CRP following Dexamethasone for HCs), whether they have a key comorbidity, defined as one or more of hypertension, diabetes or cardiovascular disease as covariates and treatment included as covariates.

In addition, a supplementary analysis will be fitted for the length of ICU stay, a logistic regression model will be fitted, with a 1 for the outcome if the individual had any hours in the ICU and a 0 if the individuals had no hours in the ICU, with age, gender, BMI, baseline CRP (defined as the last CRP measurement prior to randomisation, or the first CRP following Dexamethasone for HCs), whether they have a key comorbidity, defined as one or more of hypertension, diabetes or cardiovascular disease as covariates and treatment included as covariates.

- Length of ICU stay (hours) over 7 days follow-up
- Length of ICU stay (hours) over 35 days follow-up
- Time on Oxygen over 7 days follow-up
- Time on Oxygen over 35 days follow-up
- Length of hospitalisation from baseline (days)

For the "time on Oxygen" analyses, regardless of the amount of oxygen received, if there is evidence that any oxygen was provided to the participant on that day, 24 hours will be added to the time on Oxygen.

For the following secondary endpoints, descriptive summary statistics only will be presented:

- Blood pressure over 7 days follow-up
- Pulse rate over 7 days follow-up
- Temperature over 7 days follow-up
- Respiratory rate over 7 days follow-up
- Time on MV over 7 days follow-up. This will only include individuals who were on MV at any point over 7 days follow-up.
- Time on MV over 35 days follow-up. This will only include individuals who were on MV at any point over 35 days follow-up.

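### Time to discharge is censored at death, and stay, ICU and oxygen time have no death rule, so read alone these secondary results can understate or mask a difference when more patients die in one arm

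*SAP*

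**What the plan says.** **Time to discharge (SAP Section 11.2).** This is analysed to Day 35 with a Kaplan-Meier median where one exists, a log-rank test, and a Cox model adjusted for age and baseline CRP. For this endpoint "data will be censored if the participant dies prior to discharge at the date of death". The same paragraph adds that "The number of events by arm will be compared". Historical controls are censored at 35 days after baseline "or the date of the last electronic record, whichever is earlier, for the historical control group".

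**Durations (SAP Section 11.2).** ICU hours and oxygen time (each over 7 and 35 days) and length of hospitalisation are compared by covariate-adjusted linear regression. For oxygen, "if there is evidence that any oxygen was provided to the participant on that day, 24 hours will be added to the time on Oxygen". There is also, for ICU, a logistic model for any ICU time: "a supplementary analysis will be fitted for the length of ICU stay". Sections 9.2 and 11.2 allow a transformation of continuous endpoints where needed. No rule for patients who die appears here or in Section 9.1 on missing data.

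**Follow-up and mortality.** Section 4 places the final analysis after follow-up is complete, "which is the minimum of discharge, death or 35 days after randomisation". Section 2.2.2 lists mortality as its own endpoint: "Survival at Day35, mortality data collected from EPIC database for both HCs and randomised individuals". Sections 8.4 and 11.2 state that the secondary endpoints are not powered.

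**The concern.** A patient who dies in hospital can never be discharged. Censoring at death treats that patient as someone whose discharge is merely unobserved, so the Kaplan-Meier curve overstates the proportion who leave. The Cox ratio compares discharge rates among those still alive and in hospital, which is a legitimate quantity but not a comparison of how many go home.

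The durations have a related problem. A patient on oxygen every day who dies on day 4 scores about 4 × 24 = 96 hours, while a survivor on oxygen for 10 days scores 240. The shorter figure looks better.

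Unequal mortality unrelated to treatment is plausible here. Of 70 planned comparators, 60 are non-randomised (SAP Section 12), and the propensity score in SAP Section 11 does not include oxygen requirement. The direction of any imbalance is unknown. What is at stake is the reading of the discharge, stay, ICU and oxygen results when they are taken without the survival result.

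**Working it through.** **Plan figures.** The documents give no planning numbers for these endpoints. The stated total of 90 concerns CRP only. It reproduces (two-sided t-test, difference 0.40 × 99 = 39.6, SD 62, 30:60, power 0.807) and plays no part below.

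**Inputs (assumed).** Constant, independent daily hazards: discharge *d* = 0.10 in both arms; death *m* = 0.004 (comparators, n = 70) and 0.012 (active arm, n = 30); *L* = *d* + *m* = 0.104 and 0.112. The arm with more deaths is chosen only for illustration. In-hospital deaths by Day 35 are (*m*/*L*)(1 − e^(−35*L*)) = 3.7% v 10.5%, close to or within the 4–15% background mortality in Protocol Section 3.

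**Time to discharge**
- Planned Kaplan-Meier median: ln 2 / 0.10 = 6.93 days in both arms.
- Planned Kaplan-Meier proportion discharged by Day 35: 1 − e^(−3.5) = 97.0% in both arms.
- Actually discharged alive: (*d*/*L*)(1 − e^(−35*L*)) = 93.6% v 87.5%, about 66 of 70 v 26 of 30.
- Day on which cumulative incidence of live discharge reaches 50%: −ln(1 − 0.5*L*/*d*)/*L* = 7.06 v 7.33. The planned median is therefore off by 0.13 and just under 0.40 days.
- Cox ratio by simulation: 1.00 with deaths censored at death; 0.87 with deaths kept at risk to Day 35 (0.93 and 0.77 if the second arm's death hazard is 0.008 or 0.020).
- SE of the log ratio: √(1/26.3 + 1/65.5) = 0.23, so ln 0.87 = −0.14 is about 0.6 SE.

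**Length of stay (untransformed)**
- Cut at death: (1 − e^(−35*L*))/*L* = 9.36 v 8.75 days. Difference −0.61, SE 1.82, about 0.3 SE in favour of the arm with more deaths.
- Deaths scored 35 days: add *m*[35/*L* − (1 − e^(−35*L*))/*L*²] = 0.99 and 2.81, giving 10.35 v 11.56. Difference +1.21, SE 2.36, about 0.5 SE the other way.

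**Oxygen time**, assuming oxygen every day until discharge or death: 237 v 222 h over 35 days (SE 43); 126 v 123 h over 7 days (SE 12). Under that assumption it largely repeats the stay result.

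**ICU hours**, assuming ICU death hazards of 0.03 v 0.10/day: mean 29 v 19 h (SE 16.5), with deaths 3.6% v 8.0% and any ICU stay 15.2% in both arms.

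**Dependence on the assumptions**
- Second arm's discharge hazard 0.09 instead of 0.10: stay is 9.4 v 9.5 days and the planned ratio 0.90, so that arm already looks worse. The gap is still understated (10.3 v 12.5 days with deaths scored 35; ratio 0.79 with deaths kept at risk).
- A separate simulation with 15% v 4% deaths: with death independent of discharge, the ratio is 1.00 planned against 0.78 with deaths kept at risk, and the stay difference −0.8 against +2.3 days. With deaths on days 1–7 among frail long-stay patients, the ratio is 1.15 against 0.81 and the stay difference −1.6 against +1.8 days. In a further setting the planned ratio was 0.95, against 0.80.

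**The case against.** **Mortality is not hidden.** Day-35 survival stands beside time to discharge in SAP Section 11.2, with its own event counts, log-rank test and Cox model, and covers historical controls as well as randomised patients. This stands, and it confines the problem to results read alone. The safety comparison of deaths (Section 11.4) is a weaker safeguard, because its population (Section 6.4) excludes historical controls.

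**The censoring rule is pre-specified and the ratio is valid.** Agreed: it is a cause-specific ratio. What is missing is a statement to that effect, and the Kaplan-Meier median is a poor summary of time to discharge. The planned event count would partly reveal the gap (66 of 70 v 26 of 30).

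**The figures rest on a simple model.** True. Constant independent hazards are a convenience, and any threshold at which the bias changes sign would be an artefact of them. A transformation could change the mean differences. Section 4 defines follow-up rather than how durations are derived, so for stay, ICU and oxygen the point rests on the definitions and the SAP's silence.

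**The tables may already show deaths.** SAP Section 13.1 refers to a separate file of tables that is not available here. A reader might infer that no death count or cause-specific label will accompany these results. The documents do not support that; only the SAP text can be judged.

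**Conclusion.** A minor point that holds. As written, SAP Section 11.2 can show no difference, or a small advantage, for an arm with more deaths. In the illustration a ratio of 1.00 replaces 0.87, and stay of 9.4 v 8.8 days replaces 10.3 v 11.6. Every shift in that illustration is under one standard error, and its medians move by less than 0.4 days.

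Two stronger readings are tempting. One is that the arm with more deaths will necessarily look better. The 0.09/day case and the 0.95 ratio show otherwise: sign and size depend on who dies and when. The other is that the trial's conclusion is at risk. It is not, because the primary CRP analysis does not use these endpoints and the SAP calls them unpowered. Confidence is high that the distortion is possible. The magnitudes are illustrative, since all hazards are assumed.

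**What to change.** - **Time to discharge.** Keep patients who die before discharge in the risk set by censoring them at Day 35. State that for historical controls known to have died this replaces the last-record date. Report cumulative incidence of discharge alive, with death as a competing event, in place of the death-censored Kaplan-Meier median. If the cause-specific ratio is kept, label it so.
- **Length of hospitalisation to Day 35, and oxygen time over 7 and 35 days.** Add one sensitivity analysis in the planned regression model. Deaths before discharge within the window receive the maximum (35 days; 7 × 24 = 168 h or 35 × 24 = 840 h), identically in randomised participants and historical controls. Deaths after discharge keep the observed value.
- **ICU hours.** Leave as description alongside the planned any-ICU logistic model. A worst-rank score would not fit the planned regression and would gain almost nothing: under the ICU assumptions above, the chance that the higher-mortality arm scores worse moves only from 0.497 to 0.502.
- **Presentation.** Show Day-35 deaths by arm beside these results, if the table shells do not already do so.

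The cost is SAP wording and minor programming; dates of death and discharge are enough. The downside is that the maximum-time score mixes mortality with duration and adds no power.

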## **Exploristics Limited**

# Identifier: EXP20012

Clinical Study Identifier: 132333 following Dexamethasone for HCs), whether they have a key comorbidity, defined as one or more of

hypertension, diabetes or cardiovascular disease as covariates and treatment included as covariates.

- Proportion of individuals on Mechanical Ventilation (MV) over 7 days follow-up
- Proportion of individuals on Mechanical Ventilation (MV) over 35 days follow-up
- Proportion of individuals with Pneumonia over 7 days follow-up
- Proportion of individuals with Pneumonia over 35 days follow-up

For the following secondary endpoints, a linear regression model will be fitted, with age, gender, BMI, baseline CRP (defined as the last CRP measurement prior to randomisation, or the first CRP following Dexamethasone for HCs), whether they have a key comorbidity, defined as one or more of hypertension, diabetes or cardiovascular disease as covariates and treatment included as covariates.

In addition, a supplementary analysis will be fitted for the length of ICU stay, a logistic regression model will be fitted, with a 1 for the outcome if the individual had any hours in the ICU and a 0 if the individuals had no hours in the ICU, with age, gender, BMI, baseline CRP (defined as the last CRP measurement prior to randomisation, or the first CRP following Dexamethasone for HCs), whether they have a key comorbidity, defined as one or more of hypertension, diabetes or cardiovascular disease as covariates and treatment included as covariates.

- Length of ICU stay (hours) over 7 days follow-up
- Length of ICU stay (hours) over 35 days follow-up
- Time on Oxygen over 7 days follow-up
- Time on Oxygen over 35 days follow-up
- Length of hospitalisation from baseline (days)

For the "time on Oxygen" analyses, regardless of the amount of oxygen received, if there is evidence that any oxygen was provided to the participant on that day, 24 hours will be added to the time on Oxygen.

For the following secondary endpoints, descriptive summary statistics only will be presented:

- Blood pressure over 7 days follow-up
- Pulse rate over 7 days follow-up
- Temperature over 7 days follow-up
- Respiratory rate over 7 days follow-up
- Time on MV over 7 days follow-up. This will only include individuals who were on MV at any point over 7 days follow-up.
- Time on MV over 35 days follow-up. This will only include individuals who were on MV at any point over 35 days follow-up.

Continuous endpoints will be assessed for conformance to normality assumptions and the appropriate transformation will be conducted if necessary.

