For analyses relating to the primary objective, group comparisons will be performed using a repeated measures mixed model, adjusted for baseline factors and with treatment as the main effect. Prior to analysis, all endpoints will be assessed for conformance to normality assumptions and the appropriate transformation will be conducted if necessary. Some exploratory endpoints may only be available in the active treatment group. In this case, a within group analysis will be conducted to compare baseline and post-baseline measurements.

An interim analysis will be conducted when 12 participants have been randomised. The results of the interim analysis will be used to re-estimate the sample size if necessary.

3 Background and rationale

Clinical background

COVID-19 is a heterogeneous disease caused by infection with SARS-CoV-2 and although the majority of patients (80%) have mild disease, 15% will require oxygen and of these 25% will require ICU, of which 47 – 71% require ventilatory support. Risk factors for severe disease include older age, male sex, obesity and comorbid disease. There are no specific cures for COVID-19 and current care is supportive. A key challenge is to intercept patients early in the course of their disease to prevent deterioration and reduce the numbers that need ventilatory support, a life-saving treatment that is currently only available for a minority of patients.

SARS-CoV-2 is able to directly infect nasal, bronchiolar and alveolar epithelial cells resulting in lung inflammation, characterised, in severe cases, by an over-exuberant inflammatory response, shortness of breath and hypoxaemia. Once SARS-CoV-2 infection progresses to the stage of pneumonia, key pathogenic drivers result in symptoms characteristic of the acute respiratory distress syndrome (ARDS) with a high mortality.

In patients with confirmed COVID-19 pneumonia, 50% developed dyspnoea at 8 days after illness onset (range: 5–13 days). Mortality of these patients is around 4-15%, as a result of ARDS, coagulation dysfunction, and secondary infection that may result in septic shock and multi-organ failure (Zhou et al., Lancet 2020). Cytokines are thought to be key drivers of these pathological events and in particular levels of IL-6 are found to be raised in COVID-19 patients and to correlate with mortality (Gong et al., medRxiv 2020). Anti-IL-6 is seen as a potential therapy in COVID-19 following favourable reports from a clinical study in China.

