8.8 Discontinuation/withdrawal of participants

In consenting to participate in the trial, participants are consenting to trial treatment, assessments, follow-up and data collection.

Discontinuation of trial treatment for clinical reasons

A participant may be withdrawn from trial treatment whenever continued participation is no longer in the participant's best interests, but the reasons for doing so must be recorded. Reasons for discontinuing treatment may include:

- Alternative clinical diagnosis emerges (no longer considered to have primary COVID-19 lung disease).
- Disease progression whilst on therapy.
- Unacceptable toxicity.
- Intercurrent illness which prevents further treatment.
- Patients withdrawing consent to further trial treatment.
- Any alterations in the participant's condition which justifies the discontinuation of treatment in the Cl's or designee's opinion.
- Persistent non-compliance to protocol requirements.
- Participant is put on end of life pathway and dies prior to dosing.

The decision to withdraw a participant from treatment must be recorded in the CRF and medical notes, and the sponsor when required should be notified in writing.

Participant withdrawal from trial treatment or follow-up

If a participant expresses their wish to withdraw from trial treatment or follow-up, sites should explain the importance of remaining on trial follow-up and seek permission to allow use of routine follow-up data to be used for trial purposes. The importance of safety follow-up should be emphasised to the participant in the Participant Information Sheet.

The decision of the participant to withdraw from treatment or follow-up must be recorded in the CRF and medical notes.

The participant may withhold their reason for withdrawal however, if the participant gives a reason for their withdrawal, this should be recorded.

Withdrawal of consent to data collection

If a participant explicitly states that they do not wish to contribute further data to the trial their decision will be respected and recorded in the CRF and medical notes.

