#### 9. DATA HANDLING CONVENTIONS

#### 9.1 Premature Withdrawal and Missing Data

Mixed models will be used to analyse most endpoints; these models handle missing data naturally. Therefore, all available data will be included in all models.

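### The any-ICU model (explicitly) and the MV proportion models (by natural reading) count death without ICU or ventilation as a non-event, which can distort the odds ratios in either direction

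*SAP*

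**What the plan says.** SAP section 2.2.2 lists "Proportion of individuals on Mechanical Ventilation (MV) over 7 days follow-up" and "Proportion of individuals on Mechanical Ventilation (MV) over 35 days follow-up" as secondary endpoints. Section 11.2 gives the analysis: "For the following secondary endpoint, a logistic regression model will be fitted, with age, gender, BMI baseline CRP value", with key comorbidity and treatment also in the model. For length of ICU stay, the same section adds a supplementary logistic model whose outcome is 1 for any hours in the ICU and 0 for none. All secondary analyses use the primary analysis population, which section 6.1 defines as the two randomised arms plus matched historical controls.

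Death is dealt with in two other places. It is an endpoint of its own ("Survival at Day35, mortality data collected from EPIC database for both HCs and randomised individuals"), analysed by Kaplan-Meier, log-rank test and Cox model. For time to discharge there is a stated rule: "data will be censored if the participant dies prior to discharge at the date of death". The only missing-data text, section 9.1, concerns mixed models ("these models handle missing data naturally. Therefore, all available data will be included in all models") and does not mention death. No composite of MV or ICU with death is planned. The WHO ordinal score covers randomised participants only, over 7 days.

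**The concern.** The protocol's background (section 3) gives the clinical purpose as stopping patients from progressing to ICU and ventilatory support. The MV and any-ICU proportions are the most direct measures of that purpose. In both, a patient who deteriorates and dies on the ward would carry the same value as one who goes home well. A lower MV proportion could then reflect fewer deteriorations, or more deaths without ventilation, and the model cannot tell these apart. The reverse also holds: many unventilated deaths among the comparators would lower their MV proportion and hide a benefit.

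Randomisation would limit chance and systematic differences in who is ventilated before death, but most comparators are not randomised. Matching and model adjustment use age, gender, BMI, baseline CRP and key comorbidity. They do not use calendar period, limits placed on treatment, or access to ventilation. The comparisons split by control source in SAP section 8.3.1 are planned for the primary endpoint only.

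**Working it through.** **1. How a death is scored**

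- *Any ICU:* the outcome is 0 when there are no ICU hours. A death without ICU is therefore 0. This follows from the written definition.
- *MV over 7 or 35 days:* the outcome is whether the patient was on MV in the window. A patient who died without MV was not on MV, so the natural coding is 0. No sentence says so, and none says otherwise.
- *Time to discharge:* death has its own rule. The authors considered death for one endpoint in section 11.2 but wrote no rule for the binary ones.

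**2. Who is compared**

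SAP section 12 plans 30 dornase alfa, 10 randomised BAC and 60 historical controls. Comparators: 10 + 60 = 70, of whom 60/70 (6 in 7) are not randomised.

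**3. Rough scale from the protocol**

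The documents give no expected MV rate or power for this endpoint, so there is no figure of the plan's own to reproduce. From the background section, among patients needing oxygen 25% need ICU, and 47% to 71% of those need ventilatory support: 0.25 × 0.47 = 0.1175 and 0.25 × 0.71 = 0.1775, about 12% to 18%. Mortality in confirmed pneumonia is given as 4% to 15%. The denominators differ, and 4% to 15% is all deaths, not unventilated deaths. These figures set an order of magnitude only.

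**4. MV odds ratio when MV-or-death is the same in both groups**

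Let C be the proportion with MV or death, M the mortality, and s the share of deaths that occur without MV. Then MV proportion = C − M × s. C and M are equal in the two groups, so the MV-or-death odds ratio is 1.00. Assumed: C = 20% or 30%; s = 75% in the dornase alfa group and 25% in the comparators. M is taken from the protocol's range.

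| M | C | MV, dornase alfa | MV, comparators | MV odds ratio | Odds ratio with shares reversed |
|---|---|---|---|---|---|
| 4% | 20% | 17.0% | 19.0% | 0.87 | 1.15 |
| 4% | 30% | 27.0% | 29.0% | 0.91 | 1.10 |
| 15% | 20% | 8.8% | 16.3% | 0.49 | 2.02 |
| 15% | 30% | 18.8% | 26.3% | 0.65 | 1.54 |

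Third row in full: 0.20 − 0.15 × 0.75 = 0.0875; 0.20 − 0.15 × 0.25 = 0.1625; odds ratio = (0.0875/0.9125)/(0.1625/0.8375) = 0.49. With s = 50% in both groups every MV odds ratio is 1.00.

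**5. Two cases with MV inside the 12% to 18% range**

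- MV 12% v 18%, deaths without MV 10% v 4%: MV odds ratio (0.12/0.88)/(0.18/0.82) = 0.62. MV-or-death is 22% v 22%, odds ratio 1.00. An apparent benefit disappears.
- MV 12% v 12%, deaths without MV 4% v 10%: MV odds ratio 1.00. MV-or-death is 16% v 22%, odds ratio (0.16/0.84)/(0.22/0.78) = 0.68. A possible benefit is hidden.

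**6. Precision**

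With 30 v 70 patients, deaths without MV of 10% v 4% are about 3 v 3 patients (30 × 0.10 and 70 × 0.04 = 2.8). The odds ratio of 0.62 would have an approximate unadjusted 95% confidence interval of 0.18 to 2.19. A distortion of this size lies well within sampling error, but it does move the point estimate.

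**The case against.** *Deaths are reported anyway.* Day 35 survival is collected for both sources, with events by arm, a log-rank test and a Cox model, so an excess of deaths would be seen beside the MV result. That stands in part. The survival analysis does not show which deaths were unventilated, so the MV odds ratio cannot be corrected from it. The WHO ordinal score does not fill the gap, because it leaves out historical controls and stops at Day 7.

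*The endpoint is secondary, unpowered and largely descriptive.* True. This limits the priority of the point, but an adjusted model is still planned and its estimate may be read.

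*Eligibility and matching already help.* Terminal disease and life expectancy under 12 months are exclusions, applied to historical controls where the data exist, and matching covers age and comorbidity. This should reduce the number of patients unlikely to be ventilated, and the imbalance in them. It does not remove either.

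*Differing access to ventilation is not shown.* This stands. A reader might take the protocol's remark that ventilation is "a life-saving treatment that is currently only available for a minority of patients" as evidence of rationing in one of the groups. It is general background and says nothing about either group. A reader might also take the controls to be the earliest admissions. The SAP calls the database the first 120 patients, yet sets the controls' baseline at the first CRP after dexamethasone, which the protocol's account of BAC (section 6.5) does not list. Their calendar period is therefore unclear.

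*The end-of-life wording does not help the concern.* This also stands. Protocol section 8.8 has "Participant is put on end of life pathway and dies prior to dosing" among reasons for stopping trial treatment. Such a patient would usually have no post-baseline CRP and so fall outside the primary analysis population. The line does not show the plan foreseeing unventilated deaths in the MV analysis.

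*MV data are weak.* The SAP version log (version 1.5) records that MV incidence could not be derived reliably. A composite inherits this in its MV part.

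**Conclusion.** The concern holds in a limited form. The any-ICU model scores death without ICU as 0 by its written definition. The MV models do the same for death without MV by natural reading, not by a stated rule. No planned analysis combines either outcome with death.

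The resulting odds ratios can be distorted if deaths without ventilation or ICU are distributed differently between the dornase alfa group and the comparators. The size is unknown. The range of about 0.5 to 2.0 needs mortality near 15%, MV-or-death at 20%, and unventilated shares of 75% v 25%; at 4% mortality the same shares give 0.87 to 1.15. The shares and the MV-or-death rates are assumptions. With equal shares, and equal mortality as assumed here, there is no distortion.

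A reader might infer that the plan makes the drug look better than it is. The documents do not support a direction: the same arithmetic can hide a benefit. Nor do they support the inference that the MV proportion should be dropped or demoted. Incidence of MV is a protocol secondary endpoint (sections 4 and 11.1.2), and reporting it remains proper. The point concerns the analysis only and implies nothing about who should be ventilated.

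**What to change.** Keep the MV proportion over 7 and 35 days as listed. In SAP section 11.2:

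- Add logistic models for MV or death, and for ICU admission or death, by Day 7 and by Day 35, with the covariates already specified. Make these the basis for any statement about preventing ventilation or progression to ICU.
- State how death without MV is scored in the MV proportion.
- Tabulate MV alone and death without MV for the dornase alfa group and separately for each control source (randomised BAC, historical).
- State how historical controls whose last electronic record precedes Day 35 are counted. The survival analysis censors them, but a binary outcome needs its own rule.

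The cost is SAP wording, four derived variables (two composites in two windows) and one table. No new data are needed, since MV and ICU data and mortality are already to be used for both sources. The composite also has more events to model: in the third row of the table above, 2.6 + 11.4 = 14 expected MV events against 20 with MV or death among 100 patients. The downsides are that the composite mixes two different events, which the component table makes visible, and that its MV part carries the data limitation recorded in the SAP log.
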